6.4 Accountability Procedures for the Study Product

The research pharmacy will be responsible for maintaining logs (paper or electronic) to document the acquisition and dispensing of Erenumab and placebo. The pharmacy will also be responsible for maintaining and monitoring storage conditions. The logs and records of storage conditions will be reviewed by the study clinical monitor during periodic monitoring visits.

6.5 Assessment of Subject Compliance with Study Product Administration

Participants will receive the medication or placebo injection by a trained study staff member once a month on Visits 1, 2 and 3.

Between visits, study personnel will contact participants by telephone to assess study drug tolerance (AEs), and to remind them when they are scheduled for another dosage.

6.6 Concomitant Medications/Treatments

At the Screening and Baseline Visit (Visit 0), information concerning prior and concomitant medications for the previous 30 days will be collected, including name(s) of medication(s), total daily dose, start date, stop date (if applicable), and primary reason for use. Similarly, information about prior and concomitant therapies, including injection therapy (nerve blocks, botox), will also be collected for all participants for the 30 days prior to the Screening and Baseline Visit. The concomitant medication/therapy information will also be updated at subsequent study visits (Visits 1-5).

6.6.1 Allowable Pain Medication

6.6.1.1 Prescription medications

Participants who enter the study already on a daily regimen of a prescription medication for the management for trigeminal neuropathic pain or for other type of pain in other region of the body will be encouraged to continue that regimen throughout the study and it should not be modified. The usage of all prescription medications for pain during the study will be recorded and quantified at each visit.

Rescue medications will be defined as over-the-counter topical anesthetics and over-the-counter analgesics and anti-inflammatories. In case a patient presents pain, the medications described below may be used.

6.6.1.2 Over-the-counter medications

Topical anesthetics can be used as a rescue strategy for pain exacerbations. Benzocaine 20% to use intraorally (orabase) or lidocaine 4% (aspercreme with lidocaine) to use extraorally could be used. Participants using these topical non-prescription anesthetics during the study, will be recorded and their use will be quantified at each visit; the usage will be classified as either episodic or daily.

Episodic use of non-prescription analgesics and anti-inflammatories (acetaminophen, NSAIDs) will be defined as use for no more than 2 consecutive days and for no more than 18 days from baseline to visit 4. This type of analgesics should not be used for more than 2 days a week prior to Baseline and a week prior to V4, when the exploratory outcome is assessed.

If a participant is taking an over-the-counter medication daily for management of any type of pain or for prophylaxis of myocardial infarction or stroke, the participant will be encouraged to continue the same usage of that medication throughout the study.

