6.6.4 Not allowed medications

Participants cannot take as rescue medication or start therapy with any oral antiepileptics, SSRIs, SSNRIs, MAOIs, tricyclics antidepressants, tizanidine, baclofen, prednisone during the study (Please see Appendix B). In addition, they cannot receive any nerve blocks, onabotulinum toxin A injections, or use prescription compound topicals (except the ones that can be used as rescue mentioned above) or drug infusions for the management of TNP.

Participants who are currently taking pain medication for TNP and the rescue medication was not helpful and are in need of other strategy due to TNP, they will need to be withdrawn from the study to follow up with TNP management (this being dosage adjustment of the medication they are currently taking for the management of TNP or other).

Participants who are not currently taking pain medication for TNP, and the rescue medication was not helpful and are in need of other strategy. They will need to be withdrawn from the study to follow up with TNP management.

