Extraoral chair side QST: The cotton swab test will test sensitivity to non-painful mechanical stimulation (low-sensitivity). With the use of a cotton swab, the skin will be gently stroked 3-4 times with strokes of 1-2 cm in length in the area of V1, V2 and V3 and we will compare responses between the non-painful side to the painful side to detect normosensitivity, hyposensitivity, hypersensitivity and allodynia.

The spatula test will test temperature sensitivity following the same procedure as in the other 2 tests and temperature will be applied for 2-3 seconds. It is performed with a spatula that will be cold not exceeding 5 degrees Celsius or heated in a water bath until is 40 degrees Celsius.

EEG Assessment

EEG assessment will be performed in all participants. In chronic pain patients, alpha rhythms are slower in frequency and elevated in power relative to matched, healthy controls[39, 40]. Within the alpha band, the frequency at which maximum power is displayed, known as peak alpha frequency (PAF), varies considerably amongst individuals [45]. We have shown that PAF predicts future pain sensitivity in multiple experimental pain models [41-43]. We will examine whether erenumab can modulate PAF and therefore mediate clinical effects. PAF is based on a 5-minute, eyes-closed resting state EEG.

Daily Symptom Diary

Participants will be asked to complete the Daily Symptom Diary at the end of each day starting at the baseline phase and through the entire study (visits 1-5). Participants should have at least 80% compliance with the DSD the entire month, the equivalent of 23 completed days.

The diary collects the participant's pain intensity (reported on a 0-10 numeric rating scale) and use of pain medication. Participants are required to complete a Daily Symptom Diary electronically or on paper and a new form will be used for each month of the study. These forms may be returned in person at study visits.

Outcome Measure Questionnaires

Listed in the Schedule of Events (Appendix A). Questionnaire forms on paper will be provided to the participants if an electronic form is not feasible.

Some questionnaires are self-administered, and others will be administered by trained study staff.

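### No timing rule keeps rescue lidocaine 4% off the facial skin before the facial QST, mainly at Visit 4

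*Combined protocol and SAP*

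**What the plan says.** Section 6.6.1.1 defines rescue as two groups of over-the-counter products: topical anaesthetics, and analgesics with anti-inflammatories. Section 6.6.1.2 treats them in separate paragraphs.

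- **Topicals.** Benzocaine is allowed in the mouth and, on the face, "lidocaine 4% (aspercreme with lidocaine) to use extraorally could be used". Use is recorded and quantified at each visit, and "the usage will be classified as either episodic or daily". No maximum number of days and no interval before testing is given.
- **Acetaminophen and NSAIDs.** After defining episodic use of these drugs, the section adds "This type of analgesics should not be used for more than 2 days a week prior to Baseline and a week prior to V4". The stated reason is that the exploratory outcome is assessed at that time.
- **Daily users.** A participant "taking an over-the-counter medication daily for management of any type of pain" is encouraged to continue unchanged. Inclusion criterion 8 says the same for daily OTC pain medication.
- **Prohibited topicals.** Section 6.6.4 says participants may not "use prescription compound topicals (except the ones that can be used as rescue mentioned above", so the rescue topicals are exempt.

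The extraoral QST in section 8.1 strokes facial skin in the three trigeminal areas with a cotton swab. The purpose is to "compare responses between the non-painful side to the painful side to detect normosensitivity, hyposensitivity, hypersensitivity and allodynia". A cold or warm spatula follows by the same procedure. QST is listed at Visit 0 (section 7.2) and Visit 4 (section 7.3.4).

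**The concern.** The plan accepts that rescue medication can disturb the exploratory assessment, and it limits oral analgesics for that reason. It sets no such condition on the one extraoral rescue drug that works by numbing the skin under test.

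Numbed skin on the painful side can be classed as hyposensitive, or can lose its allodynia, for reasons unrelated to erenumab. Allodynia is a named exploratory measure in the Protocol Summary. For as-needed users, the change from Visit 0 to Visit 4 could then mix local anaesthesia with a real change in sensitisation.

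**Working it through.** The point concerns a missing rule. The plan states no figure to reproduce, so the check sets the sections side by side.

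1. **Does the existing cap cover lidocaine?** Read literally, no. The cap refers back to acetaminophen and NSAIDs, and topicals stand in the paragraph before. Read broadly, it would include topicals but would still allow use on 2 of the 7 days, and nothing excludes the day of testing. The gap remains under both readings.

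2. **Does another section close it?** Section 6.6.4 exempts the rescue topicals. The procedure lists in sections 7.2 and 7.3.4 contain no topical check before QST. No section sets a washout, a same-day hold or a rule for rescheduling.

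3. **When does exposure arise?** Criterion 7 asks as-needed OTC users to stop before Visit 0. Topical rescue is permitted afterwards, up to and including the day of Visit 4. As-needed users are therefore exposed mainly at Visit 4. Daily users continue throughout and may be exposed at both visits. Section 7.5 repeats the Visit 4 procedures at early termination, although Appendix A marks no QST there. If section 7.5 governs, that visit is a further occasion.

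4. **Who and what is affected?** Criterion 3 admits intraoral or extraoral pain. Only participants with extraoral pain have a reason to put lidocaine on the tested skin, and only the painful side is in question. The finger-probe and forearm heat tests are at other sites. EEG, cytokines and the primary and secondary endpoints do not use the facial readings.

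5. **Could an affected reading be identified later?** In part. On the diary, section 8.1 states: "The diary collects the participant's pain intensity (reported on a 0-10 numeric rating scale) and use of pain medication". Concomitant medication is updated at Visits 1 to 5 (section 6.6), so the day of use is probably traceable. The time and site of the last application are not asked for anywhere. Section 12.3 allows rescue history as a covariate if necessary, but that cannot show whether a given patch of skin was numb when tested.

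6. **How large is the effect?** It cannot be computed. The documents give no rate of topical use, and neither the strength nor the duration of the effect of lidocaine 4% on these tests. What follows from section 12.2 is only the weight of one participant. With 20 per arm it is 100/20 = 5.0 percentage points. With 15% dropout, 20 × 0.85 = 17 per arm, and the weight is 100/17 = 5.9 points. This is a scale for reading the facial categories, not an estimate of bias.

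**The case against.** The strongest reply is that skin preparation before a bedside test belongs in a test procedure rather than a protocol. Section 2.3.1 says that QST staff will be trained and calibrated, and section 16.6 mentions a Manual of Procedures, which is not among the documents. Topicals are allowed equally in both blinded arms, use is recorded, rescue history is an optional covariate, and the outcome is exploratory in a 40-person pilot.

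Much of this stands. It fixes the severity at minor, and if the manual already holds such a rule, a cross-reference is enough. It does not remove the point. The protocol expressly permits the conflicting use, and neither the diary nor the covariate gives time or site. Equal permission is also not equal use: rescue follows randomisation and may differ by arm if erenumab relieves pain.

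A reader might infer more than the documents support:

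- **That the facial QST comparison is biased in a known direction or amount.** The documents do not show who will use lidocaine, in which arm, or when. More use on placebo would make that arm look less allodynic and mask a benefit; more use on erenumab would do the reverse. An assumed usage rate turned into a probability would measure only the assumption.
- **That QST as a whole, or the main result, is compromised.** The hand and forearm tests are at other sites, and the primary endpoint is diary pain.
- **That oral analgesics are banned on the test day while lidocaine is not.** The existing rule is a weekly frequency cap.
- **That topical use goes unrecorded.** It is recorded; only the time and site of the last application are missing.

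**Conclusion.** The concern holds as a minor gap in conduct. The plan as written allows painful-side facial QST on anaesthetised skin, mainly at Visit 4, and does not collect what is needed to recognise such readings. The consequence is limited to painful-side facial QST in participants with extraoral pain, which is part of one exploratory endpoint. The size and direction of any bias are unknown.

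The conclusion assumes that lidocaine 4% can dull touch or temperature sensation at the site of application, which is its purpose as a topical anaesthetic. It also assumes that no document outside the protocol already sets the rule.

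**What to change.** - **Rule.** Add to section 6.6.1.2 that topical anaesthetic should not be applied to the facial skin to be tested on the day of Visit 0, Visit 4 or any early termination visit where QST is done, until the facial QST is finished.
- **Daily users.** They only postpone that day's application until after the test and otherwise continue unchanged. This keeps the rule compatible with criterion 8.
- **Record.** At the concomitant-medication step, which sections 7.2 and 7.3.4 already list before QST, record the time and site of the last topical application.
- **If it was on tested skin.** Delay the facial QST that day where possible. Otherwise keep the reading, flag it, and report flagged counts by arm.
- **Visit 0.** Consent is signed at that visit and pre-screening may coincide with it, so some participants cannot be told in advance. For them, delay or flag.

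No separate sensitivity analysis is needed. Section 12.3 names linear mixed models for continuous outcomes and no specific test for the facial categories, so there is no defined main analysis for it to accompany.

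The cost is two or three eCRF items, an occasional delayed test and a brief hold on one rescue option. A participant who needs the topical may still use it; the facial test is then delayed or flagged.

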6.6.4 Not allowed medications

Participants cannot take as rescue medication or start therapy with any oral antiepileptics, SSRIs, SSNRIs, MAOIs, tricyclics antidepressants, tizanidine, baclofen, prednisone during the study (Please see Appendix B). In addition, they cannot receive any nerve blocks, onabotulinum toxin A injections, or use prescription compound topicals (except the ones that can be used as rescue mentioned above) or drug infusions for the management of TNP.

Participants who are currently taking pain medication for TNP and the rescue medication was not helpful and are in need of other strategy due to TNP, they will need to be withdrawn from the study to follow up with TNP management (this being dosage adjustment of the medication they are currently taking for the management of TNP or other).

Participants who are not currently taking pain medication for TNP, and the rescue medication was not helpful and are in need of other strategy. They will need to be withdrawn from the study to follow up with TNP management.

6.6.5 Nonpharmacologic Therapy

<30 March 2022>

During the course of the study, participants will not be restricted in the use of non-pharmacological therapies, excluding Cognitive Behavioral Therapy (CBT) and acupuncture. If a participant starts these for the complementary management of pain during the study, the use of these therapies will be recorded in the eCRF and the patient will need to be withdrawn of the study.

7 STUDY SCHEDULE

7.1 Pre-Screening

Pre-screening (0-2 weeks, Day -15 to -1)

Potential participants may be contacted by telephone or in person for pre-screening; in some instances, it may also be conducted simultaneous with the Screening and Baseline Visit (Visit 0) or during a scheduled visit to the Brotman Facial Pain Clinic, Oral Surgery Clinic or Pain Medicine Clinic (School of Medicine).

After contacting potentially eligible participants and after obtaining their verbal consent we will proceed to conduct a pre-screening interview with questions designed to identify participants with a high probability of meeting inclusion criteria. This interview will be conducted by trained study staff using a standard script. For the potential participants who express interest in the study, documentation of verbal consent, the pre-screening date, and screening ID will be recorded. In addition, an in-clinic Screening and Baseline Visit (Visit 0), will be scheduled within 2 weeks from the date of the pre-screening interview.

7.2 Screening and Baseline Visit (Visit 0, 4 weeks period)

This visit will happen with 2 weeks after pre-screening. Participants will start the baseline period that will consist of 4 weeks.

- Obtain and document consent from subject participation in the study.
- Obtain signed Health Insurance Portability and Accountability Act (HIPAA)

Authorization

- Review medical/dental history to determine eligibility based on inclusion/exclusion criteria.
- Take blood pressure and collect weight and height.
- Review medications history to determine eligibility based on inclusion/exclusion criteria.
 - Record concomitant medications and therapies
- Perform QST examination
- Perform EEG
- Collect blood for Cytokine release assay

- - Perform urine pregnancy test (in women with childbearing potential)
 - Provide instruction to complete 4 outcome measure questionnaires in paper or electronically for review next visit
 - Provide instruction to complete Daily Symptom Diaries electronically or in paper dispense forms.

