These assessments will be performed on 2 clinic visits. It is expected that these assessments will evoke brief pain or discomfort within a range that is acceptable for the participant. Transient redness or tenderness of the skin may appear after these assessments but none of them is expected to result in lasting discomfort or tissue damage. In addition, the participants may request to stop the examination/test at any time. These assessments will end upon the completion of the modality or upon the participant's request, whichever comes first.

EEG assessment. Peak alpha frequency (PAF): There is no potential risk or harm in the EEG assessment. PAF is based on a 5-minute, eyes-closed resting state EEG. The EEG device will be placed on the Scalp of the participants and EEG data will be collected using a CGX quick8r dry electrode system. Participants will be asked to make facial muscle contractions such as clenching their teeth, blinking, and saccades, while EEG is recorded. Participants may find uncomfortable the EEG device as well as the facial contractions, but these may only induce transitory discomfort. The facial contractions are necessary because will be used to aid in automated artefact removal. Participants will then be told to relax their muscles and resting state eyes closed EEG will be recorded for 5 minutes and used for PAF calculation.

Questionnaires: It is possible that some participants may experience discomfort associated with answering several questionnaires as well as with being asked personal questions about his/her emotional state and feelings, health history or symptomatology. The participants will be informed that they can choose not to answer any question for any reason.

Blood collection: Participants may find the blood draw unpleasant and there is a possibility of mild pain and bruising associated with it. Trained personnel will perform the blood draw using standard procedures. If for any reason the blood draw is being difficult (i.e. finding a vein) and the subject/patient is uncomfortable, the blood draw will be stopped immediately. The participants will be informed that they can choose to stop the blood collection for any reason.

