5 STUDY ENROLLMENT AND WITHDRAWAL

The study is planning to enroll a total of 40 subjects that will be randomly assigned to one of the two study groups. It is anticipated that a total of 200 subjects will be screened in order to meet recruitment goals.

Participants will be pre-screened in person at the Brotman Facial Pain clinic, the Oral and Maxillofacial Surgery Clinic both at the University of Maryland, School of Dentistry, Pain Medicine Clinic at the University of Maryland, School of Medicine or by telephone.

Vulnerable subjects: No specific vulnerable populations are being targeted for recruitment for this study.

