5.4.1 Randomization Procedures (if applicable)

Extensive screening procedures of potential participants to determine their eligibility based on the inclusion and exclusion criteria will be carried out prior randomization. Participants who do not meet these criteria will not be enrolled in the study.

Randomization visit will be within 7 days after Baseline Phase period has finished (4 weeks/28 days), eligibility will be further confirmed based on completion of Daily Symptom Diaries and pain intensity score. Qualified participants will be randomly assigned to one of the two arms of the study in a 1:1 ratio:

- 1) Investigational arm: Erenumab: N= 20 participants
- 2) Placebo: N=20 participants

Randomization

Subjects will be randomized to the investigational treatment group (Erenumab) or the placebo group using a blocked randomization scheme. The examiners and patients will be blind to the group assignment. Randomization will be done by Investigational Drug Services (IDS/Research pharmacy). There will be a 1:1 ratio of treatment to placebo participants.

Blinding

Blinding will be done by Investigational Drug Services (IDS). The PI and study staff will be blind to what the participant is receiving.

Treatment/randomization codes

IDS will be responsible for randomization of participant assignment to either the study medication or placebo groups. IDS will use a random number generation program to determine assignment.

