7.2.1 Randomization

The participant to be eligible requires to present symptoms of trigeminal neuropathic pain for a minimum of 3 months (12 weeks). In addition, the participant to be eligible is required to have 80% compliance with the Daily Symptom Diary for the baseline period after visit 0 and reported an average pain intensity score of 4/10 in where 0= no pain and 10= maximum pain imaginable on a numerical rating scale (0-10), during the 4 weeks/28 days baseline period prior randomization as specified in the inclusion criteria. Participants then will be randomly assigned to one of two groups (Erenumab or placebo) and will be scheduled for Visit 1. Visit 1 should be scheduled within a week after randomization.

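### Exploratory endpoints only: QST and EEG are done at Visit 0, before the diary run-in decides randomisation; testing at Visit 1 before the injection would be closer to treatment and would spare run-in failures a test expected to hurt

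*Combined protocol and SAP*

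**What the plan says.** Section 7.2 lists "Perform QST examination" and the EEG among the Visit 0 procedures. Appendix A marks both at V0 and V4 and nowhere else apart from the early-termination provision in 7.5. Sections 3.1 and 3.2.2 use them only for exploratory objectives, and neither appears in the criteria of 5.1 or 5.2.

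The diary starts after Visit 0. Section 7.2.1 requires "80% compliance with the Daily Symptom Diary for the baseline period after visit 0" and a mean pain score of 4/10 over the same 28 days before anyone is randomised. Section 5.4.1 then says "Randomization visit will be within 7 days after Baseline Phase period has finished (4 weeks/28 days", and 7.2.1 adds "Visit 1 should be scheduled within a week after randomization". The first injection is given at Visit 1 (7.3.1), which has no QST or EEG.

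On numbers, section 5 says "The study is planning to enroll a total of 40 subjects" and "It is anticipated that a total of 200 subjects will be screened in order to meet recruitment goals". On burden, 2.3.1 says of QST: "It is expected that these assessments will evoke brief pain or discomfort within a range that is acceptable for the participant". The same section describes the EEG as carrying no potential risk.

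**The concern.** Tests that serve only a baseline-to-Visit-4 comparison are done before it is known who will enter that comparison. This has two consequences.

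First, the exploratory baseline is further from the first dose than it needs to be. If QST and peak alpha frequency drift within a person over weeks, a more distant baseline correlates less with Visit 4 and the treatment contrast is estimated less precisely, in a trial of only 40. It also sits before the diary month that serves as the pain baseline, whereas at Visit 4 the tests come at the end of the matching diary month.

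Second, people who fail the run-in have had pain-evoking stimuli, and the plan describes no analysis of non-randomised participants. Visit 1 is attended only by randomised participants, so testing there would avoid this.

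**Working it through.** **Lag from exploratory baseline to first dose.** Inputs: 28 diary days (7.2.1), 0 to 7 days to randomisation (5.4.1), 0 to 7 days to Visit 1 (7.2.1).

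- Minimum: 28 + 0 + 0 = 28 days. Maximum: 28 + 7 + 7 = 42 days.
- Check against the plan's own figure of 21 weeks from Visit 0 to Visit 5 (section 4), with Visit 5 on Day 112: 28 + 112 = 140 days (20 weeks) and 42 + 112 = 154 days (22 weeks). The stated 21 weeks lies inside this range and implies a lag of 147 − 112 = 35 days.
- Visit 0 to Visit 4 (Day 84): 112 to 126 days, of which 28/112 = 25% to 42/126 = 33% precede any dose.

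**People tested but never randomised.** 200 − 40 = 160. This ceiling is reached only if every one of them attends Visit 0, passes the history and medication review, is tested and then fails the run-in or withdraws. The documents give no split. If 25%, 50% or 75% of the 160 drop out before QST (assumed), then 120, 80 or 40 are tested without being randomised.

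**Precision.** Section 12.3 tests continuous exploratory outcomes by the group-by-time interaction. With only a baseline and Visit 4 measured, that is essentially a difference in change scores. Let ρ0 be the correlation of Visit 4 with a Visit 0 baseline, and ρ1 that with a Visit 1 baseline, assuming equal variances. The ratio of standard errors, Visit 0 to Visit 1, is:

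- change scores: √[(1 − ρ0)/(1 − ρ1)]
- baseline-adjusted: √[(1 − ρ0²)/(1 − ρ1²)]

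The documents give no correlation, so a range is needed.

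*(a) Correlation constant over time:* ρ0 = ρ1, ratio 1, loss 0%.

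*(b) Geometric decay by r per 28 days (assumed):* ρ1 = r³, and ρ0 = r⁴ for a 28-day lag or r^4.5 for a 42-day lag.

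| r | Lag (days) | ρ0 | ρ1 | Change-score ratio | Adjusted ratio |
|---|---|---|---|---|---|
| 0.7 | 28 | 0.240 | 0.343 | 1.075 | 1.033 |
| 0.7 | 42 | 0.201 | 0.343 | 1.103 | 1.043 |
| 0.9 | 28 | 0.656 | 0.729 | 1.127 | 1.103 |
| 0.9 | 42 | 0.622 | 0.729 | 1.180 | 1.143 |

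The loss is about 8 to 18% for change scores and 3 to 14% with baseline adjustment.

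*(c) Mixed structure (assumed: 0.6 of the variance stable, 0.2 decaying by 0.7 to 0.9 per 28 days, 0.2 measurement error):* ρ = 0.6 + 0.2 × the decay term. The loss is about 3 to 5% for change scores and 2 to 4% with adjustment. Example, r = 0.8 and a 42-day lag: ρ0 = 0.673, ρ1 = 0.702, change-score ratio √(0.327/0.298) = 1.048.

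**The case against.** The strongest answer is that nothing here is invalid. The Visit 0 baseline precedes randomisation and follows one rule for both arms. A reader might infer that the untreated weeks contaminate the drug effect, but drift before dosing is expected to be the same in both groups and cancels in the comparison. Only precision is at stake, and only for exploratory outcomes. This stands.

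The size of the loss depends on the assumed correlation. The participant random effect planned in 12.3 corresponds to constant correlation, where the loss is zero. That is a working model and 12.3 allows other covariance structures, so it does not show the loss to be zero, but the range must start there.

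A reader might also infer that 160 people would be tested to no purpose. The documents do not support this. A screening ID is assigned at pre-screening (7.1), which may be by telephone, so the 200 may include people who never attend Visit 0. Pre-screening is meant to select likely eligible people, and 7.2 lists "Review medical/dental history to determine eligibility based on inclusion/exclusion criteria" ahead of QST. The EEG is described as harmless, so the burden argument rests on QST, which the participant can stop at any time.

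Nor are the Visit 0 tests without information on analgesic use. Section 6.6 records medication for the previous 30 days, and inclusion criterion 7 in 5.1 has as-needed pain medication stopped before that visit.

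Finally, the chairside sensory test in 8.1 is the only sensory examination listed at Visit 0. No section uses it for diagnosis, but if it is so used in practice it has a reason to stay.

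**Conclusion.** The point holds as a cheap improvement to the exploratory part of the plan, not as an error that threatens its conclusions. QST and EEG precede the run-in that decides randomisation, and their baseline lies 28 to 42 days before the first dose. Those who fail the run-in undergo QST with no planned use of the data. How many is unknown: at most 160 of 200, probably far fewer.

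The randomised comparison is unbiased and the diary-based endpoints are unaffected. The loss of precision for change scores lies between 0% and about 18% of the standard error. The upper figure requires geometric decay with no stable between-person component, an assumption the documents neither state nor support. The lag itself rests only on the plan's own windows and is firm.

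**What to change.** Move QST and EEG from the list in 7.2 to 7.3.1, to be completed at Visit 1 before the injection and under blind. Move the two Appendix A marks from V0 to V1, and name the Visit 1 values in 12.3 as the baseline for these outcomes. If the chairside sensory test is in fact used for diagnosis at Visit 0, keep that part there and say so.

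In the same amendment, reconcile three places that bear on the exploratory baseline:

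- Cytokine blood draw: Visits 0 and 4 in 7.2, 8.1 and Appendix A, but Visits 1 and 4 in 8.2.2.
- Appendix A timing of Visit 0: 4 weeks before Visit 1 in the first part, 1 to 3 weeks in the second, which heads the QST and EEG rows. The second cannot hold with a 28-day diary.
- Analgesic limit in 6.6.1.2: it is tied to Baseline and to Visit 4. State which date Baseline means once the tests are at Visit 1, so that the passage and the test date agree.

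Cost: a protocol amendment and a longer Visit 1. A randomised participant who misses or fails the Visit 1 tests would have no exploratory baseline, so the plan should say how such a participant is handled. The number of baseline test sessions falls to at most 40. If the sponsor prefers Visit 0, a sentence giving the reason would suffice.
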